6.3.4.4. Statistical methods: analysis of count data with overdispersion

The incidence rate and its 95% CI will be estimated using the Generalised Linear Model (GLM) assuming a negative binomial distribution for the response variable with logarithm as link function and the logarithm of follow up time as an offset variable. The fit of the model will be examined using Q-Q plots of standardised residuals. It is possible that the negative binomial model will not converge due to underdispersion of data; in such cases, to overcome the problem of underdispersion, a Poisson model will be used to obtain the incidence rate and its 95% CI.

SAS codes:

```
proc genmod data = <dataset>;
  class gold age smoking exacHist;
  model n_exac = GOLD age smoking exacHist country
    / link=log dist=negbin offset=logfuinyears ;
  ods output parameterestimates=out_parm nobs=nobs;
  ods exclude modelinfo modelfit parameterestimates nobs;
  run;

  data parm_est(keep= val rate rate_ll rate_ul);
    set out_parm(where=(parameter='intercept'));
    format rate rate_ll rate_ul 8.2;
    val= "mean number per year from negative binomial model without
covariate";
    rate=exp(estimate);
    rate_ll=exp(lowerwaldcl);
    rate_ul=exp(upperwaldcl);
  run;
```

where GOLD = COPD grade (2, 3 or 4), age = age at enrolment (40-49, 50-59, 60-69, ≥ 70 years), smoking = smoking status at enrolment (current and former smokers), exacHist = number of exacerbations reported in the 12 months prior to enrolment (one, two and equal or above three), country = countries in the study (Hong Kong, Philippines, Korea, Taiwan), n_exac = number of exacerbations during the study and logfuinyears = logarithm of the follow-up period in years.

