160	160	1.00	0.85	1.15	0.81	1.19	0.78	1.22
190	190	1.00	0.86	1.14	0.83	1.17	0.80	1.20
2 AECOPD/ subject/ year			95% CI*		95% CI*		95% CI*	
T	n	Value (n/T)	LL	UL	LL	UL	LL	UL
40	80	2.00	1.56	2.44	1.46	2.54	1.38	2.62
130	260	2.00	1.76	2.24	1.70	2.30	1.66	2.34
160	320	2.00	1.78	2.22	1.73	2.27	1.69	2.31
190	380	2.00	1.80	2.20	1.75	2.25	1.72	2.28
3 AECOPD/ subject/ year			95% CI*		95% CI*		95% CI*	
T	n	Value (n/T)	LL	UL	LL	UL	LL	UL
40	120	3.00	2.46	3.54	2.34	3.66	2.24	3.76
130	390	3.00	2.70	3.30	2.64	3.36	2.58	3.42
160	480	3.00	2.73	3.27	2.67	3.33	2.62	3.38
190	570	3.00	2.75	3.25	2.70	3.30	2.65	3.35

* Normal approximation with variance = $\Phi n/T^2$, where Φ is the overdispersion factor for a Poisson distribution (calculations performed in Microsoft Excel).

T = Total number of evaluable subjects; n = Total number of exacerbations; CI = confidence interval; LL = lower limit; UL = upper limit.

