6.2. Analysis of primary objective

The analysis of the primary objective will be performed on the FAS.

Average proportion of patients with sputum samples positive for bacterial or viral pathogens overall and for specific species, and its exact 95% confidence interval (CIs) will be computed at any stable scheduled visit and at any exacerbation visit for the entire study period. In addition, the average proportion of sputum samples positive for bacterial and viral pathogens overall and for specific species, and its 95% confidence interval will also be computed at any stable scheduled visit and at any exacerbation visit for the entire study period. Confidence intervals will be estimated using a Generalized Estimating Equations (GEE) model assuming a binomial distribution for the response variable with logit as link function and a compound symmetry correlation matrix (exchangeable structure) to account for the within-patient correlations (Liang, 1986) (more details in section 6.2.1). If the GEE model will not run due to only one level of the outcome variable, the exact 95% confidence interval will be computed. Proportion of patients with sputum samples positive for bacterial/viral pathogens overall and for specific species, will be computed, with exact 95% CIs, at each stable* scheduled visit (visit 1, visit 2, visit3) and at each exacerbation visit confirming acute exacerbation**.***.

* A confirmed stable visit will be defined as a scheduled study visit for which the investigator confirms in the eCRF that the patient is stable/has recovered from a previous exacerbation.

** If an AECOPD occurs at the time when one of the scheduled [stable] study visits is planned, it should be handled and recorded as an AECOPD visit. If possible, the stable study visit should be re-scheduled to a later date, within the ± 14 days' time window from the scheduled appointment, when the patient is stable again.

*** The definition of acute exacerbation of COPD (AECOPD) event is detailed in section 12.

CONFIDENTIAL

201112 (EPI-NTHI-001 BOD APA)
 Statistical Analysis Plan Amendment 2 Final

In details the following pathogens will be evaluated:

- Bacteria including, but not necessarily limited to, *H. influenzae**, *M. catarrhalis*, *S. pneumoniae*, *S. aureus*, *P. aeruginosa*, *K. pneumoniae* and *A. baumannii* by bacteriological methods (culture).

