6.3.4.2. Incidence bacteria/viruses associated AECOPD

The following incidence rates (per patient per year) will be computed, with 95% CIs:

- AECOPD events with sputum sample containing bacterial pathogens found by culture or by PCR (overall and by, but not limited to, the following bacterial species: *H. influenzae* (and *H. influenzae* after differentiation from *H. Haemolyticus* by PCR assay), NTHi (after differentiation from typeable *H. influenzae* by PCR assay), *M. catarrhalis*, *S. pneumoniae*, *S. aureus*, and *P. aeruginosa*).
- AECOPD events with sputum sample containing viral pathogens found by PCR (overall and by, but not limited to, the following viral species: RSV, parainfluenza virus, enterovirus/ HRV, metapneumovirus, influenza virus, adenovirus, bocavirus and coronavirus using qualitative PCR and HRV also by quantitative RT-PCR).

These incidence rates, with 95% CIs, will be estimated also according to covariates such as COPD severity, sex, country, age at enrolment, smoking status at enrolment and number of exacerbations reported in the 12 months prior to enrolment.

In addition, incidence rate of mild, moderate and severe exacerbation having sputum containing any bacterial/viral pathogen will be computed overall and by species.

Incidence rate of AECOPD overall and associated to bacteria (detected by culture and by PCR) will be computed also at interim analysis.

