11.5. Methodology for computing CI

- All CI computed will be two-sided at 95% significant level.
- The exact 95% CIs for a proportion within a group will be calculated using Clopper Pearson method [[Clopper 1934](#)].

12. ANNEX 2: AECOPD DEFINITION AND CALCULATION RULE**12.1. Definition, onset, recovery, duration of an AECOPD event**

AECOPD events are confirmed according to investigator judgment after an AECOPD visit which is aimed to exclude worsening in symptoms not related to an AECOPD event.

AECOPD visits are scheduled after an electronic Diary Card alert confirmed by the investigator (by phone call or at the study site) or after spontaneous site visits due to worsening symptoms without any alert.

Electronic Diary Card alerts refer to daily symptoms recorded the morning after (also called morning symptoms). Alerts are based on the Anthonisen criteria:

- Worsening of two or more of the following major symptoms for at least two consecutive days*^{***}: dyspnea, sputum volume, sputum purulence (colour)

Or

- Worsening of any major symptom together with any of the following minor symptoms for at least two consecutive days*^{***}: sore throat, colds (nasal discharge and/or nasal congestion), fever (oral temperature $\geq 37.5^{\circ}\text{C}$) without other cause, increased cough, increased wheeze.

** The same two symptoms do not have to be present on both days as long as at least one major symptom is present on both days.*

CONFIDENTIAL

201112 (EPI-NTHI-001 BOD APA)
 Statistical Analysis Plan Amendment 2 Final

AECOPD onset will be defined as the first day of the two consecutive days of worsening symptoms.

AECOPD recovery will be determined/confirmed by the investigator/delegate during (a) follow-up phone call(s) which will take place every 2 weeks until the AECOPD has resolved. The end date will be based on when the investigator/delegate determines that the AECOPD symptoms have resolved. In determining this end date, consideration will be given to symptoms recorded in the electronic Diary Card and patient assessment during the phone calls.

AECOPD duration will be defined as the number of days from AECOPD onset (included) and AECOPD recovery (not included).

Duration = date2 – date1 + 1,

with date2: AECOPD recovery date,

date1: AECOPD onset date

12.2. Recovery and duration of an exacerbation according to EXACT-PRO:

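### SAP 6.3.4.4 yields no usable 95% confidence interval for an AECOPD rate in a cell with no events, and it credits the Poisson fallback with correcting underdispersion when it only cures non-convergence

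*SAP*

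**What the plan says.** SAP 6.3.4.4 fits a generalised linear model "assuming a negative binomial distribution for the response variable with logarithm as link function", with log follow-up time as offset. The sample code exponentiates the Wald limits of the intercept; the lower-limit line begins "rate_ll=exp(lowerwaldcl". The section then anticipates one failure: "It is possible that the negative binomial model will not converge due to underdispersion of data". In that case, "to overcome the problem of underdispersion, a Poisson model will be used to obtain the incidence rate and its 95% CI". It names no scale factor, robust variance or exact method, and does not mention cells without events.

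SAP 6.3.4.2 applies these rates to individual bacterial and viral species, splits them by COPD severity, sex, country, age, smoking and exacerbation history, and adds that "incidence rate of mild, moderate and severe exacerbation having sputum containing any bacterial/viral pathogen will be computed overall and by species".

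For proportions, SAP 6.2 does foresee a degenerate outcome: "If the GEE model will not run due to only one level of the outcome variable, the exact 95% confidence interval will be computed". SAP 11.5 sets the level ("All CI computed will be two-sided at 95% significant level") and gives an exact method, Clopper-Pearson, for proportions only.

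**The concern.** Two things look wrong, and they differ in weight.

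- **Empty cells.** A log-link model cannot represent a rate of zero. A programmer following 6.3.4.4 literally would print the last iterate of a diverging fit, or a blank. For a rare pathogen in a small subgroup, the upper limit is the only information the cell holds, and it would be lost or improvised.
- **Rationale of the fallback.** A Poisson model fixes the variance at the mean. It is the zero-dispersion limit of the negative binomial, so it removes the parameter that fails to converge, but it does not describe data that vary less than Poisson. The SAP sentence claims more than the model delivers.

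Pathogen-associated AECOPD rates with 95% CIs are planned under the secondary objectives (Protocol 9.6, SAP 6.3.4.2).

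**Working it through.** **Inputs from the documents.** Two-sided 95% limits (SAP 11.5). Log-link model with exponentiated Wald limits (SAP 6.3.4.4). 160 evaluable subjects for 200 enrolled, dispersion Φ of 1, 1.5 or 2, one AECOPD visit per subject, 80% with evaluable sputum, and 5% as the lowest positivity tabulated (Protocol 9.2, Tables 12 and 13). Four countries (SAP 2).

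**Inputs assumed here.** One year of follow-up per patient, so T patients give T patient-years; an equal split over countries, giving 160/4 = 40; cell rates of 0.02 and 0.05 per year; a small cell of T = 20; and Φ values below 1.

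**1. The plan's own figure.** Table 13 uses n/T ± 1.96·√(Φn)/T. For n = T = 160 and Φ = 1 this is 1 ± 1.96 × 12.65/160 = 0.85 to 1.15, as printed. All 48 intervals in the table reproduce. None uses Φ below 1 or n = 0.

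**2. Zero events.** The Poisson score equation requires the fitted total T·exp(b) to equal the observed total, 0, so b has no finite solution. Each Newton step is b + (0 − μ)/μ = b − 1. Starting from log(0.5/40) = −4.38, 25 steps give b = −29.38 and SE = 1/√(40·exp(b)) = 3.79 × 10⁵. The exponentiated limits are 0 and numerical overflow. The negative binomial likelihood with all counts zero is also maximised as the mean goes to 0, so it fails in the same way. This was hand-coded, not run in SAS, which would print its own last iterate.

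**3. How likely an empty cell is.** P(0) = exp(−rate × T) for Poisson counts. Overdispersion at the same mean makes zeros more likely.

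| Rate per year | T = 20 | T = 40 | T = 160 |
|---|---|---|---|
| 0.02 | 67% | 45% | 4% |
| 0.05 | 37% | 14% | <0.1% |

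The protocol's planning figures give an intermediate case: 1 × 0.80 × 0.05 = 0.04 per year, so exp(−1.6) = 20% at T = 40. SAP 6.3.4.2 names 7 bacterial categories and 8 viruses. With 3 + 2 + 4 + 2 + 2 + 3 = 16 subgroup levels (two age groups, as in SAP 6.3.4.1) and 3 exacerbation severities, that is 15 × 16 + 15 × 3 = 285 cells.

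**4. Exact limit for an empty cell.** Upper limit = χ²(0.975; 2 df)/(2T) = 3.69/T, which is 0.184 for T = 20, 0.092 for T = 40 and 0.023 for T = 160.

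**5. Width of the plain Poisson limits if true Φ is below 1.** On the log scale they are too wide by 1/√Φ: 3% at 0.95, 5% at 0.9, 12% at 0.8 and 41% at 0.5. Large-sample coverage is 95.6%, 96.1%, 97.2% and 99.4%. When every patient has 0 or 1 event, Φ = 1 − mean. With T = 160, n = 8 gives 0.025 to 0.100 plain against 0.025 to 0.098 scaled at Φ = 0.95; n = 32 gives 0.141 to 0.283 against 0.147 to 0.273 at Φ = 0.8.

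**6. Fallback triggered by chance.** In 20,000 simulated sets of 160 truly Poisson counts, taking sample variance at or below the mean as a stand-in for non-convergence:

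| Mean | Variance ≤ mean | Plain coverage in those sets | Scaled coverage in those sets |
|---|---|---|---|
| 0.05 | 82% | 96.0% | 96.0% |
| 0.2 | 59% | 95.7% | 94.1% |
| 1.0 | 56% | 94.9% | 94.0% |

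**The case against.** The best defence is that Poisson is the natural model to fall back on. It repairs the failure the SAP describes, and its limits err on the safe side. Working step 6 supports this: when the trigger is chance rather than real underdispersion, plain Poisson is about nominal, and scaling by the estimated dispersion falls slightly short at the two higher means. This stands, and it removes any case that the fallback has to be replaced.

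A reader might infer that the reported limits are too wide in general, by 12% to 20%. The documents do not support that. The excess exists only where the fallback is used and true Φ is below 1. Excesses of 12% and 20% arise if no patient has a second event at 0.2 or 0.3 per year. For Poisson counts in 160 patients that has probability [exp(−m)(1 + m)]¹⁶⁰, about 6% and 0.2%. At 0.05 per year it is about 82%, but the excess there is 2.6%.

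A reader might also infer that the uncorrected Poisson model would be applied to overdispersed data whenever the negative binomial fails. The SAP limits the fallback to underdispersion; for other failures it states no rule. Earlier SAP versions had a Poisson adjustment for overdispersion, but that text is superseded and is not evidence of an error.

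On empty cells, the defence is that their frequency depends on assumed rates and an assumed split, and that SAP 6.3.5 reports counts and rates by species and by severity without a model. Both are fair. But 6.3.5 does not ask for species within country or GOLD grade, and a visible zero count still lacks its upper limit. The gap remains.

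**Conclusion.** The zero-event gap is real. Followed as written, 6.3.4.4 gives no usable interval for any cell without events, and no exact alternative for rates appears elsewhere in the SAP. How many cells are affected depends on true rates and cell sizes that the documents do not give; across the assumed range the chance per cell runs from negligible at 160 patient-years to well over one third in small subgroups. The exact limit itself assumes Poisson counts, since dispersion cannot be estimated from a cell of zeros.

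The underdispersion point is one of wording and interpretation: the limits are conservative, not invalid. SAP 7 treats every analysis as descriptive and no decision rule uses these limits, so the consequence is confined to the precision shown in the tables. The change is worth making because the affected cells are foreseeable and the SAP already accepts the same principle for proportions.

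**What to change.** 1. Add to SAP 6.3.4.4, with a matching line in 11.5: for any cell with zero events, the rate is reported as 0 with the exact two-sided 95% Poisson interval, lower limit 0 and upper limit 3.69 divided by the patient-years in the cell.
2. Reword the fallback sentence to say that Poisson is used because the negative binomial did not converge, that it does not model underdispersion, and that its limits are conservative if true dispersion is below 1. Flag the tables where it was used.
3. Optionally, show a robust (by patient) or Pearson-scaled variance as a sensitivity analysis. It need not replace plain Poisson.

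The cost is two or three SAP sentences and a short programming branch for zero counts. No new data are needed.

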6.3.4. Incidence rates of AECOPD

This study will provide an estimate of average number of exacerbations per person per year, in a COPD population at increased risk of exacerbation (i.e. moderate to very severe COPD patients with a documented history of at least 1 moderate or severe AECOPD in the year prior to enrolment).

To compute the incidence rate all the exacerbations will be taken into account. The observation period is from visit 1 to visit 3 or from visit1 to the last visit performed for patients lost to follow up.

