6.3.4.1. Overall incidence

The following incidence rates (per patient per year) will be computed, with 95% CIs [using negative binomial regression detailed in section [6.3.4.4](#)]:.

- Confirmed exacerbations (exacerbation events confirmed by the investigator plus missed exacerbation visits with medical records: 5 and 6 dash boxes for the former and 2 and 7 for the latter from [Figure 1](#)).
- Confirmed exacerbations plus potential exacerbations with alert confirmed by phone call/or at the study site (potential exacerbations correspond to 3 dash box in Figure 1).
- Exacerbation events with sputum sample positive for selected pathogens

CONFIDENTIAL

201112 (EPI-NTHI-001 BOD APA)
 Statistical Analysis Plan Amendment 2 Final

The incidence rate of confirmed exacerbations and of confirmed exacerbations plus potential exacerbations confirmed by phone call/or at the study site, with 95% CIs, will be estimated according to COPD severity at enrolment based on GOLD classification [GOLD 2, 3, 4].

The incidence rates of confirmed exacerbations, with 95% CIs, will be also computed by exacerbation severity.

In addition, the incidence rates of confirmed exacerbations, with 95% CIs, will be estimated according to covariates such as sex, country, age at enrolment (below median age or equal to/above median age), smoking status at enrolment (current and former smokers) and number of exacerbations reported in the 12 months prior to enrolment (one, two and equal or above three).

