6.3.4.1. Overall incidence

The following incidence rates (per patient per year) will be computed, with 95% CIs [using negative binomial regression detailed in section [6.3.4.4](#)]:

- AECOPD events clinically confirmed by the investigator (5 and 6 dash boxes in [Figure 1](#)).
- Confirmed exacerbations (AECOPD events plus missed AECOPD visits with medical records: 2, 5, 6 and 7 dash boxes in [Figure 1](#)).
- Potential AECOPD with alert confirmed by phone call/or at the study site (2, 3, 5, 6 and 7 dash boxes).

The incidence rate of AECOPD events, AECOPD events plus missed AECOPD visits with medical records and potential AECOPD confirmed by phone call/or at the study site, with 95% CIs, will be estimated according to COPD severity at enrolment based on GOLD grade [moderate, severe, very severe].

The incidence rates of AECOPD events and AECOPD events plus missed AECOPD visits with medical records, with 95% CIs, will be also computed for mild AECOPD, moderate AECOPD and for severe AECOPD.

In addition, the incidence rates of confirmed exacerbations (events and AECOPD events plus missed AECOPD visits with medical records), with 95% CIs, will be estimated according to covariates such as sex, country, age at enrolment (40-49, 50-59, 60-69, ≥ 70 years), smoking status at enrolment (current and former smokers) and number of exacerbations reported in the 12 months prior to enrolment (one, two and equal or above three).

An attempt to control simultaneously for all the above mentioned variables/factors will be done with multivariable negative binomial regression.

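### The SAP 6.3.4.4 code fits five covariates but reports exp(intercept) as the covariate-free mean rate, so it does not give the overall AECOPD incidence

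*SAP*

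**What the plan says.** SAP 6.3.4 sets the target: "This study will provide an estimate of average number of exacerbations per person per year". SAP 6.3.4.1 lists the overall rates, to be computed with 95% CIs "using negative binomial regression detailed in section" 6.3.4.4.

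The prose of SAP 6.3.4.4 describes a negative binomial model with a log link and log follow-up time as offset. Protocol 9.6 describes the same model. Neither names a covariate, and neither rules covariates out.

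The SAS code in SAP 6.3.4.4 does the following:

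- It declares "class gold age smoking exacHist" as categorical. Country is not in that list, although the variable key defines it by four place names.
- It fits "model n_exac = GOLD age smoking exacHist country" with the offset.
- It keeps one row of the estimates: "set out_parm(where=(parameter='intercept".
- It exponentiates that estimate and its Wald limits, and labels the result "mean number per year from negative binomial model without" covariate.

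The key under the code defines age in four bands. SAP 6.3.4.1 now uses two groups: "age at enrolment (below median age or equal to/above median age".

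**The concern.** All-cause AECOPD incidence is a secondary objective, and this is the only method the SAP gives for its rates and CIs. The code block contradicts itself: the MODEL line has five covariates and the output label says there are none.

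It does not work as a covariate analysis either. It discards every covariate row, omits sex (which SAP 6.3.4.1 lists) and uses different age groups from that section. No reading makes the block agree with SAP 6.3.4.1.

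The serious risk is a silent one: code adjusted just enough to run, covariates left in, producing a plausible number that is reported as the cohort mean.

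**Working it through.** **1. What the code estimates.** The model is log(expected count) = b0 + covariate terms + log(follow-up years). Exp(b0) is therefore the yearly rate when every covariate term is zero: the reference level of each CLASS variable and, if country is numeric, country = 0. It equals the cohort mean only if the covariates have no effect or their effects happen to cancel. The block has no LSMEANS, ESTIMATE or standardisation step. Without covariates, exp(b0) is the overall rate, which is what the label describes.

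**2. Likely origin.** The MODEL line is identical in SAP Version 1 and SAP Amendment 1. In both of those superseded texts, section 6.3.4.1 also planned: "An attempt to control simultaneously for all the above mentioned variables/factors will be done with multivariable negative binomial regression". The current 6.3.4.1 has dropped that sentence. The line looks left over; the older texts are context only.

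**3. The code exactly as printed.** On general SAS behaviour, a character country variable outside CLASS stops the procedure. The row filter uses a lower-case initial, whereas the GEE code in SAP 6.2.1 uses a capital, so it may select nothing. SAP 6.2.1 also shows a correct intercept-only MODEL line.

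**4. The plan's own precision figure.** The documents give no output for this code. The nearest figure is protocol Table 13 (T = 160, n = 160, Φ = 1): n/T ± 1.96 × √(Φn)/T = 1.00 ± 1.96 × √160/160 = 1.00 ± 0.155, which reproduces the printed 0.85 to 1.15. All 48 intervals in that table reproduce.

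**5. Illustrative size.** Everything in this step is assumed, for code already altered to run:

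- 200 patients, overall rate 1.0 per year, dispersion 1, 500 datasets per scenario.
- 80% followed for 1 year, the rest uniformly 0.1 to 1 year.
- GOLD 2/3/4: 45/40/15%. History 1/2/≥3: 60/25/15%. Age bands: 5/20/40/35%. Smoking: 35/65%. Four equal countries.
- Where effects are present, rate ratios are GOLD 1/1.3/1.6, history 1/1.4/2.0, and country 1/1.25/1.6/2.0 or the reverse.
- The last level is the reference.

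The arithmetic for GOLD and history effects shows the mechanism. The mean GOLD factor is 0.45 + 0.40×1.3 + 0.15×1.6 = 1.21. The mean history factor is 0.60 + 0.25×1.4 + 0.15×2.0 = 1.25. The reference cell (GOLD 4, history ≥3) then has rate 1.6×2.0/(1.21×1.25) = 2.12, against a cohort mean of 1.00. The simulated medians, with median 95% limits where shown, were:

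| Assumed effects | Country numeric 1–4 | Country numeric 0–3 | Country in CLASS |
|---|---|---|---|
| None | 0.91 (0.36–2.21) | 0.93 (0.40–2.10) | 0.90 |
| GOLD, history | 2.00 (0.84–4.75) | 1.98 (0.91–4.31) | 2.02 |
| Country rising with code | 0.49 (0.20–1.23) | 0.63 (0.27–1.47) | 1.26 |
| Country falling | 1.64 (0.65–4.21) | 1.28 (0.56–3.02) | 0.64 |
| All, country rising | 1.11 (0.45–2.66) | 1.39 (0.61–3.05) | 2.76 |
| All, country falling | 3.52 (1.52–8.11) | 2.77 (1.28–5.94) | 1.38 |

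The intercept-only model gave 0.99 to 1.00 in every scenario, with lower limits of 0.80–0.81 and upper limits of 1.22–1.23.

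With no effects, the median log-scale standard errors were 0.466, 0.424 and 0.443 for the three covariate models and 0.103 for intercept-only. The ratios are 0.466/0.103 = 4.5, 0.424/0.103 = 4.1 and 0.443/0.103 = 4.3.

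**6. Different assumptions.** A second simulation used 160 patients, all with one year of follow-up, dispersion 0.5 and numeric country. With no effects it gave 0.94 (0.42–2.04), against 0.99 (0.82–1.21) for intercept-only. Rate ratios per level of 1.2 (GOLD) and 1.3 (history) gave 1.64, and the CI covered the true overall rate 73% of the time. Ratios of 1.3 and 1.5 gave 2.18, with 45% coverage. Intercept-only coverage was 92–97% in all its scenarios.

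**The case against.** The strongest reply is that this is an editorial slip in a code sketch. SAP 6.3.4.1 cites a method, the prose of 6.3.4.4 and protocol 9.6 give that method, and the label shows that no covariates were intended. Other SAP code is loose too: the Cox block in 6.3.5.2.1 lacks a semicolon and calls itself an example. The printed code would probably fail visibly. SAP 6.3.5 also reports a crude rate that would show a discrepant model rate, SAP 8.1 requires a dry run for the final analysis, and SAP section 7 calls all analyses descriptive. The simulated effects are invented, and the widest range needs country coded 1 to 4.

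Much of this stands as a limit on the harm. The intent can be inferred, working programs may already be correct, and the range says nothing about this trial's data. The dispersion values are also assumptions, but at rate 1.0 they give variance-to-mean ratios of 1 + 1 = 2 and 1 + 0.5 = 1.5, both among the factors in protocol Table 13.

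None of it makes the text right. The example caveat applies to the Cox code only. The prose does not exclude covariates, so it does not settle the conflict. The crude rate in SAP 6.3.5 has no planned CI. SAP 8.1 requires no dry run for the interim analysis, where incidence is also computed.

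**Conclusion.** The concern holds. The contradiction between the MODEL line and the label is on the page and depends neither on the simulation nor on SAS behaviour. Followed literally, the code gives an error, an empty table, or a reference-cell rate labelled as the overall mean.

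The size in this trial cannot be known from the documents. Under the assumptions above the reported value could lie well below or well above the true rate, and where there is no bias the CI is still several times too wide; that ratio depends on the assumed covariate mix. Moving country into CLASS does not cure it, because the covariates remain.

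The production programs are not visible and no wrong result is shown. This should be corrected before incidence is reported; it does not undermine the design.

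**What to change.** For each overall rate, print `model n_exac = / dist=negbin link=log offset=logfuinyears;` and exponentiate the `Intercept` row with its limits.

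For the subgroup rates in SAP 6.3.4.1 and 6.3.4.2, state one approach: one-factor models with exponentiated LSMEANS and 95% CIs, or intercept-only fits by subgroup. Put country in CLASS where it is a factor, and split age at the median as SAP 6.3.4.1 does. Give the Poisson fallback the same structure.

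Then confirm that the production programs for the interim and final analyses match. The cost is a short SAP edit and a program check, with a rerun if they differ. No new data are needed.
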